Animal models have provided substantial evidence to support this stress neuroadaptation thesis in addiction (22–24,26–28). However, programmatic laboratory research that examines the stress response in nicotine deprived and non-deprived smokers is necessary to confirm that our understanding of stress neuroadaptations from animal models translate to addiction etiology in smokers. In particular, this application focuses on the negative affective response to aversive stressors. [name] and his colleagues have argued persuasively that negative affect is the core motivational element of the human drug withdrawal syndrome across addictive drugs including nicotine (21,29). Unfortunately, much of what we know about these motivationally critical affective processes in humans is based on a narrow range of measures collected in isolation. Moreover, complementary methods (e.g., laboratory task manipulations, clinical treatment interventions) and measurement approaches (e.g., psychophysiology, ecological momentary assessment) are rarely combined.

The research in this application capitalizes on recent research with both animals and humans that has synthesized precise laboratory manipulations of stress with sensitive psychophysiological measurement of startle reflex potentiation to parse the negative affective response to stressors into its constituent components (30,31). In particular, startle potentiation during uncertain (vs. certain) threats holds promise as a biomarker of stress neuroadaptation following chronic nicotine or other drug use (32–34).

We propose to measure stress neuroadaptation in the laboratory via startle potentiation during uncertain threat in a validated cued threat task among nicotine deprived and non-deprived smokers. Smokers will be subsequently assigned to receive active or placebo combination Nicotine Replacement Therapy with counseling only. Smokers will report (4x daily) on their experience of episodic stressors, negative affect, smoking urge, and smoking during 3 weeks (1 week pre-quit/2 weeks post quit) of a smoking cessation attempt via ecological momentary assessment.

AIM 1: Confirm stress neuroadaptation in smokers following chronic tobacco use. This stress neuroadaptation will be manifest in two contrasts for startle potentiation measured in a laboratory cued threat task that manipulates threat uncertainty.

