1.1: Nicotine deprived smokers will display selectively increased negative affect measured via startle potentiation during uncertain (vs. certain) threat relative to non-deprived smokers.

AIM 2: Examine the impact of stress neuroadaptation on negative affect, smoking urge, and smoking in response to stressors. Laboratory startle potentiation measures of stress neuroadaptation will predict ecological momentary assessment measures of:

2.1 ...overall levels of negative affect and urge
2.2 ...within-smoker covariation (i.e., coupling) of episodic stressors with negative affect, urge, and smoking (i.e., stressor-induced negative affect, urge and smoking).

AIM 3: Examine the impact of this stress neuroadaptation on smoking during the first two weeks of smoking cessation.

3.1: Laboratory startle potentiation measures of stress neuroadaptation will predict overall smoking during the first two weeks post-quit as well as measures of point prevalence abstinence and continuous abstinence measured at 2 weeks post-quit.

AIM 4: Determine if treatment of withdrawal via NRT reduces the influence of stress neuroadaptation.

4.1: Combo NRT with counseling (vs. placebo NRT with counseling) will reduce startle potentiation measures obtained at one week post-quit.

4.2: The effect of combo NRT (vs. placebo NRT with counseling) on smoking and related outcome measures will be mediated by change in startle potentiation measures from pre-quit to post-quit.

4.3: Treatment of withdrawal symptoms via combo NRT will attenuate the predictive strength of pre-quit startle potentiation measures with respect to overall levels of negative affect, urge, and smoking and stressor-induced negative affect, urge, and smoking.

RESEARCH DESIGN AND METHODS

C1: BRIEF OVERVIEW

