Three hundred participants (identified as heavy smokers) will be recruited. All participants will complete an experimental cued threat task (No shock/Predictable shock/Unpredictable shock, or NPU, as described above) designed to assess the affective components (fear, anxiety) of their response to stressors in the laboratory to test for stress neuroadaptation resulting from chronic smoking. Participants will complete the task twice in two separate experimental sessions on separate days. The first time they will be either nicotine deprived and/or non-deprived (counterbalanced). Participants are randomly assigned to one of two treatments (Combo NRT with counseling or placebo NRT with counseling) and schedule a quit date. All participants will provide 3 weeks (1 week pre-quit; 2 weeks post-quit) of 4x daily, real-time report of stressors, affective state, urge to smoke, actual cigarette use, and study medication adherence. Participants return to the laboratory at 2 weeks post-quit. At this follow-up visit, stressor exposure, affective status, withdrawal symptoms, smoking urge, tobacco use, and medication adherence will be measured. Biological confirmation (CO measurement) of recent smoking is also obtained. At the 2 week post quit visit, they complete the second administration of the experimental cued threat task.

C2: GENERAL METHODS AND MEASURES

This section provides detail on the general methods and measures in this application. A separate section (C3) details the experimental cued threat task.

C2.1: Participants. Three hundred smokers (approximately 1/3 female as represented in the Madison smoking community) will be recruited. Inclusion criteria include cigarette use ≥ 10 cigarettes/day \geq two years, smoke within the first 30 minutes of waking up, expired air carbon monoxide (CO) level ≥ 6 ppm, self-reported motivation to quit smoking, ability to read and write English, and an agreement to respond to EMA prompts throughout the day for three weeks. Health screening will ensure that participants can safely use the nicotine patch and lozenge. Specifically, participants will be excluded for FDA contraindications for NRT (e.g., no uncontrolled hypertension, recent myocardial infarction, diabetes, heart disease, asthma, stomach ulcers). All women of child-bearing potential will be required to agree to use an approved method of birth control to prevent pregnancy during the course of the study.

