The Principal Investigator will refine existing protocols for assuring data accuracy and protocol compliance. Such protocols will include data verification and protocol compliance checks as well as other quality assurance procedures. The Principal Investigator will also be responsible for ensuring that the data for the project are securely stored, that storage is in compliance with University and federal regulations and that no unauthorized persons have access (electronic or physical) to any participant-identifiable data.

STATISTICAL CONSIDERATIONS

In this section, we outline general strategies for analysis of startle potentiation, EMA, and treatment outcome that are used to address our four aims. We sketch out clear exemplars of analysis options for this rich dataset. Of course, there are numerous supplemental analyses that space constraints prevent describing here.

ANALYSIS OF STARTLE POTENTIAION (AIM 1). The analysis of startle potentiation for Aims 1 & 1.1 across experimental tasks can be accomplished within very similar General Linear Models (GLMs). In each analysis, startle potentiation will be analyzed in a GLM with Threat Uncertainty (low vs. high probability for Threat Probability task; fixed vs. variable duration for Threat Duration task) as the focal within-subject factor.

Analysis of Aim 1.1 will use the full sample as a focal between-subject factor. Support for the stress neuroadaptation thesis following chronic tobacco use would be offered by a Smoking Group X Threat Uncertainty interaction with selectively greater startle potentiation among smokers in uncertain threat for each task. Analysis of Aim 1.2 will use both pre-quit sessions and include Deprivation Status (nicotine deprived vs. non-deprived) as a focal within subject factor. Support for the stress neuroadaptation thesis when nicotine deprived would be offered by a Deprivation Status X Threat Uncertainty interaction with selectively greater startle potentiation among deprived smokers in uncertain threat for each task.

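### The Aim 1 test assigned to chronic smoking has no comparison group, and the deprivation test that remains is written for sessions the design does not provide

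*Combined protocol and SAP*

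**What the plan says.** **Statistical Considerations, analysis of startle potentiation (Aim 1).** Two analyses are given.

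- The first is numbered 1.1: "Analysis of Aim 1.1 will use the full sample as a focal between-subject factor". Its criterion is: "Support for the stress neuroadaptation thesis following chronic tobacco use would be offered by a Smoking Group X Threat Uncertainty interaction", with the larger potentiation expected in smokers under uncertain threat.
- The second is numbered 1.2: "Analysis of Aim 1.2 will use both pre-quit sessions and include Deprivation Status (nicotine deprived vs. non-deprived) as a focal within subject factor". Its criterion is a Deprivation Status by Threat Uncertainty interaction.
- Threat Uncertainty is defined through the Threat Probability and Threat Duration tasks.

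**Specific Aims, Aim 1.** The aim announces two contrasts: "This stress neuroadaptation will be manifest in two contrasts for startle potentiation measured in a laboratory cued threat task that manipulates threat uncertainty". Only one follows, numbered 1.1: "Nicotine deprived smokers will display selectively increased negative affect measured via startle potentiation during uncertain (vs. certain) threat relative to non-deprived smokers". There is no sub-aim 1.2.

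**Population (C1, C2.1).** "Three hundred participants (identified as heavy smokers) will be recruited". "Inclusion criteria include cigarette use ≥ 10 cigarettes/day", kept up for at least two years, with expired CO of at least 6 ppm. No non-smoking or light-smoking group appears in the design.

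**Sessions (C2.2, C2.3, C3).** Participants are randomized to a deprived or a non-deprived condition. The non-deprived group does the task once before quitting. The deprived group does it the day after the quit attempt starts. Everyone repeats it two weeks after quitting. C2.3 nevertheless says the sessions support within-subject tests of deprivation.

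**Task (C1, C3.1).** The task administered is the NPU task, with no-shock, predictable-shock and unpredictable-shock conditions.

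**Sample size (C4.3).** The calculation concerns the Deprivation Status by Threat Uncertainty interaction: 142, rounded up to 150 per treatment group, 300 in total.

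**The concern.** The analysis section separates two claims. The Smoking Group test is meant to support adaptation from long-term tobacco use. The deprivation test is meant to support an effect that appears when smokers go without nicotine. Only the deprivation test has a comparison group. The title of Aim 1, however, speaks of long-term use.

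Two things are at stake. First, an analyst following the text meets a model that cannot be fitted, and would have to drop it or improvise a substitute once data are in hand. Second, the surviving contrast could be read as answering the chronic-exposure question. It compares smokers about a day into abstinence with smokers who are still smoking, and it says nothing direct about how smokers differ from people without that exposure.

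The surviving test also cannot be run as written, because nobody has two pre-quit sessions. As the text stands, neither Aim 1 analysis matches the data that will be collected.

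**Working it through.** **1. The plan's own figure (C4.3).** Inputs: 90% power, effect size 0.10, and a model with two main effects and their interaction. Alpha is not stated; 0.05 is assumed.

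- With f² = 0.10 and u = 3 numerator df, the noncentrality needed is L = 14.17. L / f² = 14.17 / 0.10 = 141.7, which gives the stated 142.
- Adding u + 1 = 4 gives 145.7, so 146. Power at 142 is 0.892. The stated figure is reproduced within 3%.
- C4.3 calls 0.10 a squared multiple partial correlation for the interaction. Taken literally, f² = 0.10 / 0.90 = 0.111 with 1 df and L = 10.51, so L / f² = 94.6 and N is 97 to 99, depending on how many model terms are counted. Power at 142 would then be 0.976. The mismatch is conservative.

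The calculation concerns deprivation status. Smoking Group does not enter it.

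**2. Is Smoking Group by Threat Uncertainty estimable?** Let g = 1 for a smoker and t = 1 for uncertain threat. The four model columns are 1, g, t and g × t. With 300 smokers and 0 non-smokers, g = 1 in every row, so:

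- the g column equals the intercept column;
- the g × t column equals the t column.

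The rank is 2 of 4. The group effect is aliased with the intercept and the interaction with the threat effect. Recruiting more smokers does not change this.

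**3. Is Deprivation Status by Threat Uncertainty estimable?** Take one first session per person and let d = 1 if randomized to deprivation. The columns 1, d, t and d × t have rank 4 of 4. The test amounts to comparing the mean uncertain-minus-certain potentiation score between two randomized groups.

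Power for this 1-df test at partial R² = 0.10 (f² = 0.111), alpha 0.05:

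| N | Power |
|---|---|
| 150 | 0.982 |
| 300 | above 0.999 |

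At N = 300, the smallest f² with 90% power is 0.0353. That is a partial R² of 0.0353 / 1.0353 = 0.034, or d = 2 × √0.0353 = 0.38 on the difference score, assuming 1:1 allocation (the ratio is not stated).

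**4. Does the design supply the within-subject version?** The analysis section needs a deprived and a non-deprived pre-quit session from the same person. Under C2.3 and C3, a person's two sessions are:

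| Group | First session | Second session |
|---|---|---|
| Non-deprived | before quitting | two weeks after quitting, during active or placebo NRT |
| Deprived | the day after the quit attempt starts | two weeks after quitting, during active or placebo NRT |

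Nobody contributes the required pair. The second session differs from the first in time since quitting, treatment and repeat exposure to the task, so it cannot stand in for the missing one. C2.3 hands out study product after the first task, so the first-session comparison precedes treatment.

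**The case against.** The strongest reply is that the Smoking Group sentence is left-over text on which nothing depends. The only listed sub-aim, the Aim 1 session plan in C2.3 and the sample size in C4.3 all concern deprivation. On the protocol's own theory, set out at the start of Specific Aims, chronic adaptation shows itself as dysregulated affect when smokers lack nicotine, so a deprivation effect counts as support. C2.2 also collects smoking history and dependence, and the analysis section allows level of dependence as an exploratory moderator. Finally, the analysis section keeps the two claims apart, so misreporting is not inevitable.

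Most of this stands. A reader might infer that Aim 1 as a whole rests on the Smoking Group test, and hence that the trial cannot address Aim 1. The documents do not support that: the listed sub-aim is estimable and amply powered, and the plan treats a positive result there as evidence for its thesis. Nor do the documents show that a deprivation result will be misreported; that remains a risk of the wording.

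The reply does not repair the text. The void test is current analysis wording with its own success criterion, and it is the one the plan ties to long-term use. A dependence gradient among smokers is observational and exploratory, and does not replace the missing group. Calling the sentence left-over also leaves the deprivation test tied to sessions and tasks that the design does not contain.

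**Conclusion.** Wrong as written. One of the two Aim 1 analyses, the one assigned to chronic tobacco use, has 300 smokers and 0 comparators and yields no estimate at any sample size. The other is estimable as a randomized between-subject contrast at the first session, but it is specified as within-subject over sessions that do not exist, with threat uncertainty defined by tasks other than the NPU task.

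The sample size of 300 does not depend on the missing group. Power for the deprivation contrast exceeds 0.98 at the stated effect size, assuming alpha 0.05 and, for the standardized difference of 0.38, equal allocation. These figures make no allowance for lost data; C2.3 discontinues participants who fail to abstain twice.

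What Aim 1 can deliver is the effect of about 24 hours of nicotine deprivation within smokers. Evidence on chronic exposure as such is indirect.

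**What to change.** **Statistical Considerations, Aim 1**

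- Delete the Smoking Group by Threat Uncertainty analysis and the use of the full sample as a factor.
- Make Deprivation Status by Threat Uncertainty the single Aim 1.1 test. Deprivation Status is the randomized between-subject factor at the first session. Threat Uncertainty is the within-subject factor, defined by the NPU predictable and unpredictable conditions in C3.1.
- Remove the references to two pre-quit sessions and to the Threat Probability and Threat Duration tasks. Bring the within-subject sentence in C2.3 into line.

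**Specific Aims, Aim 1**

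- Change two contrasts to one, and use the number 1.1 throughout.
- Limit the conclusion to the effect of about 24 hours of nicotine deprivation within smokers. State that smokers are not compared with non-smokers and that evidence on chronic exposure is therefore indirect.

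**Cost.** Wording only, with a narrower Aim 1 claim. No change to recruitment, procedures or the total of 300.

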All participants report some demographic information, their current affective state (Positive and Negative Affect Scales-PANAS (120), provide information on a broad-band personality measure (Brief Multidimensional Personality Questionnaire- bMPQ); (121) and supplemental measures of trait affectivity relevant to individual differences in anxiety including the Intolerance of Uncertainty Inventory, (122), and the Anxiety Sensitivity Inventory (123). Individual differences in depressive symptoms will also be recorded Center for Epidemiologic Studies Depression Scale Revised (CESD-R; 125) and the Depression Anxiety Stress Scale-21 (DASS-21).

These measures are available to serve as covariates to increase power to test for focal effects on relevant outcome measures. They are also available as possible individual difference moderators in supplemental analyses. After completing the self-report measures, participants schedule their first experimental session. Participants are randomized to either a nicotine deprived or non-deprived condition and instructed to abstain from all nicotine containing products for 24 hours prior to their nicotine deprived session or to continue their normal pattern of smoking prior to their non-deprived session.

Finally, participants receive brief cessation counselling, schedule their experimental visits and quit date, and are provided with verbal and written instructions about the 3-week daily EMA survey that begins one week before their quit date.

C2.3: Laboratory Experimental Session(s)

All participants complete the cued threat task (NPU; see section C3 below) in each of two separate experimental sessions. Their first session is either nicotine deprived and non-deprived in a counterbalanced order, the final is 2 weeks post-quit. The deprived group completes their first experimental session the day after the start of their quit attempt, and the non-deprived group completes it before the start of their quit attempt. Data across the two experimental sessions will be used to provide sensitive within-subjects tests of deprivation effects on startle potentiation measures of stress neuroadaptation (Aim 1) and to address all subsequent Aims (2-4).

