our and other laboratories, shock intensity during these tasks is calibrated to each participant's individual sensitivity threshold, which is assessed prior to the main task during each experimental session to reduce individual differences (34,62,64,135). Startle potentiation is the primary dependent measure of affective response. As reviewed earlier, basic affective neuroscience research has indicated that startle potentiation is a sensitive and selective index of the neurobiological substrates of fear and anxiety, respectively, during conditions of certain vs. uncertain threat (30,72,74).

Participants in the non-deprived group will complete the task once pre-quit; in the deprived group, immediately post-quit, while both groups will also complete the task 2 weeks post-quit (counterbalanced) in separate experimental sessions separated by approximately two weeks. Task details are provided below. Task order within an experimental session is counterbalanced across all participants. We have preliminary data among 23 smokers in the context of an ongoing study that verify that smokers will tolerate multiple administrations across separate days of similar cued threat tasks.

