C3.3 Design Considerations and Justification: We carefully considered the experimental task to elicit negative affective response in the laboratory. In contrast to stressor tasks involving staged social interactions with confederates, self-disclosing speeches, or other similar tasks commonly used in social and health psychology research with humans, affective neuroscience has relied extensively on cued threat of electric shock (30,54,55,146). The cued threat task allows for increased precision/control over and parametric manipulation of cue characteristics (e.g., cue duration, cue-shock contingencies) and repeated presentation of trials that facilitate identification of psychological and neurobiological mechanisms involved in the affective response to stressors. Furthermore, comparable tasks can be used with animals and humans to encourage translation of findings from animal models to humans. In addition, a growing body of affective neuroscience research that explicitly manipulates threat uncertainty in cued threat tasks with animals and humans provides an attractive platform on which to examine etiologic mechanisms in tobacco dependence as they are relevant for treatment (see earlier reviews). Finally, we have pilot data that demonstrates the feasibility of multiple administrations of the cued threat task. In contrast, it is not clear that social stress tasks can be validly administered repeatedly (i.e., deprived or non-deprived and 2 weeks post-quit during medication) and therefore cannot fully address any but our first Aim. We believe the opportunity for conceptual replication will increase confidence in results and to extend understanding of the role of threat uncertainty in fear/anxiety.

For these reasons, we believe that the novel use of our cued threat task in this application is an innovative and impactful feature of the design. In contrast, given these limitations associated with the social stress tasks, we judged that the costs (monetary, staff resources, and participant burden) were not justified to add a social stress task to the experimental procedure at this stage of this research program.

Identification of and Protection against Risk

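### Aim 1's deprivation test is specified as within-subject, but each smoker is measured in only one randomised deprivation state, so it cannot be run as written

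*Combined protocol and SAP*

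**What the plan says.** The Aim 1 paragraph of the Statistical Considerations reads: "Analysis of Aim 1.2 will use both pre-quit sessions and include Deprivation Status (nicotine deprived vs. non-deprived) as a focal within subject factor". The hypothesis would be backed by a Deprivation Status by Threat Uncertainty interaction. Section C4.3 names that interaction as the effect being powered. It obtains N=142 for 90% power at an effect of 0.10, then rounds up to 150 per treatment group, 300 in all.

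The schedule is described in several places:

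- C2.2: "Participants are randomized to either a nicotine deprived or non-deprived condition".
- C2.3: "The deprived group completes their first experimental session the day after the start of their quit attempt", while the non-deprived group attends before quitting.
- C3 agrees: "Participants in the non-deprived group will complete the task once pre-quit; in the deprived group, immediately post-quit".
- C1: "At the 2 week post quit visit, they complete the second administration of the experimental cued threat task". C2.6 adds that this second administration takes place on combination NRT or placebo.
- C3.3 lists the administrations that the task must support: "validly administered repeatedly (i.e., deprived or non-deprived and 2 weeks post-quit during medication".

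Two other passages describe the deprivation test differently. C2.3 says: "Data across the two experimental sessions will be used to provide sensitive within-subjects tests of deprivation effects on startle potentiation measures". Aim 1.1 in the Specific Aims is worded between groups, predicting that deprived smokers show "selectively increased negative affect measured via startle potentiation during uncertain (vs. certain) threat relative to non-deprived smokers".

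**The concern.** A within-subject deprivation factor needs every smoker measured once deprived and once not deprived, under otherwise comparable conditions. The schedule gives each smoker one of those states and then a session in a third condition. The only model written down for the effect that sizes the trial therefore has no matching data.

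An analyst would have to choose a replacement. The documents point to two: a comparison across the two sessions (C2.3) and a comparison between groups (Aim 1.1). They rest on different assumptions and have different precision, and the plan does not say which is primary. Leaving that choice until the data are in hand weakens the main laboratory test of the trial. It also leaves the 0.10 effect size in C4.3 without a defined scale.

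**Working it through.** **1. Sessions available, by deprivation group.**

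| Group | Session 1 | Session 2 | Sessions before quitting |
|---|---|---|---|
| Non-deprived | before quit, smoking as usual | 2 weeks post-quit, NRT or placebo | 1 |
| Deprived | day after quit starts, 24 h abstinent | 2 weeks post-quit, NRT or placebo | 0 |

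The Aim 1 model needs both states in each smoker. Smokers who supply both as planned: 0 of 300. Reading pre-quit loosely, as a label for session 1, puts both states in the data set, but still only one per smoker.

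**2. Can the two sessions supply a within-subject test?** Subtracting session 2 from session 1 compares each smoker's deprivation state with week 2. That mixes deprivation with treatment, lapses, time since quitting and repeat testing. With a session term in the model, the deprivation effect becomes a difference-in-differences between randomised groups. It can be estimated, but it is not the analysis in the Aim 1 paragraph.

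**3. Reproducing C4.3.** Inputs: effect 0.10, 90% power, and three model terms (two main effects and the interaction). Alpha is not stated; two-sided 5% is assumed. Cohen's formula is N = L/f², with L = 14.17 for three numerator degrees of freedom. This gives 14.17/0.10 = 141.7, so 142, which matches. The match requires 0.10 to be used as f². The formula does not show whether the effect is within or between subjects.

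**4. Power of the session-1 between-subject test.** The outcome is each smoker's uncertain-minus-certain startle potentiation. Assumed: 150 per deprivation group, two-sided 5%, no dropout; noncentral t.

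- 90% power is reached at d = 0.3755. Then f² = d²/4 = 0.0353 and partial R² = 0.0353/1.0353 = 0.034.
- If 0.10 is a between-subject effect used as f², d = 2√0.10 = 0.632 and power is 99.98%. If it is read as partial R², f² = 0.10/0.90 = 0.111, d = 0.667 and power is 99.99%.
- If 0.10 is a within-subject effect used as f², d = √0.10 × √(2(1−ρ)), where ρ is the between-session correlation of the score. The documents do not give ρ, so a range is shown.

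| ρ (assumed) | d | Session 1 only | Difference-in-differences | Pooled two-session model |
|---|---|---|---|---|
| 0 | 0.447 | 97% | 78% | 97% |
| 0.3 | 0.374 | 90% | 78% | 92% |
| 0.5 | 0.316 | 78% | 78% | 88% |
| 0.7 | 0.245 | 56% | 78% | 84% |

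Relative to session 1, the standard error is multiplied by √(2(1−ρ)) for difference-in-differences and by √(1−ρ²) for the pooled model. The pooled column assumes that the deprivation groups have equal means at week 2.

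**The case against.** The best defence is that the section offers general strategies and exemplars, that Aim 1.1 already states the between-group hypothesis, and that C2.3 intends to use both sessions. The protocol also uses pre-quit loosely: C2.4.1 speaks of a pre-quit deprived session, and Aims 4.2 and 4.3 use a pre-quit startle measure for all smokers. This stands in part. It is why the point is confined to the impossible within-subject factor. It does not rescue the model, because no reading gives a smoker both states, and the references to counterbalancing in C1 and C2.3 add no session.

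A reader might infer more than the documents support:

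- *That there are no data for the deprivation hypothesis.* This depends on the strictest reading of pre-quit. Session 1 contains both randomised groups.
- *That the trial is underpowered.* This follows only if 0.10 is a within-subject effect and the between-session correlation is high. Neither is stated.
- *That models using week 2 would produce many false positives.* This needs a group difference at week 2 of a size that nothing in the documents supports.
- *That the failed-abstinence rule counts against difference-in-differences.* A stable selection shift cancels there and stays in the session-1 test. It is also small. C2.3 expects fewer than 5% to fail once and most of those to succeed on the second attempt, so losses are under about 0.05 × 0.5 = 2.5%, or 3.75 of 150.

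It is also fair to say that session 1 alone can be less precise than a model using both sessions, and that its contrast coincides with being post-quit rather than pre-quit.

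**Conclusion.** The point holds as an error of specification. The within-subject test cannot be run as written, on a strict or a loose reading of pre-quit, and it is the interaction that sizes the trial. The design can still test Aim 1.1 between randomised groups at session 1. This conclusion comes from the schedule and needs none of the power figures.

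Those figures rest on a 1:1 deprivation split, two-sided 5%, no dropout and assumed correlations. They show what the sample can detect (d about 0.38 at 90% power). They do not show a shortfall.

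The same section also refers to a Smoking Group factor, an Aim 1.2 and two threat tasks. None of these fits the smokers-only sample, the listed aims or the single NPU task in C3.1. This suggests text left from another design, so correcting one sentence would not be enough.

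**What to change.** 1. Restate the primary Aim 1.1 test as a session-1 analysis of NPU startle potentiation, taken before NRT or placebo is dispensed (C2.3). Deprivation Status as randomised is between-subject, Threat Uncertainty (predictable versus unpredictable shock) is within-subject, and their interaction is the focal test.
2. Keep any model that uses week-2 data as a sensitivity analysis, with its assumptions about week 2 written out.
3. State that deprivation at session 1 coincides with being post-quit versus pre-quit, and report losses under the failed-abstinence rule by deprivation group.
4. Remove or reconcile the Smoking Group, Aim 1.2 and two-task text in the Statistical Considerations. Reconcile A3 (older tasks said to be used here), A5 and C2.5 (measures from both deprivation states, unless meant at group level), C2.3 (within-subject tests) and C2.4.1 (a pre-quit deprived session) with the two-session NPU schedule.
5. Restate C4.3 for the between-subject test: N=300, the deprivation split, alpha, and 90% power at d about 0.38 (partial R² about 0.034). Say whether 0.10 is a between- or within-subject effect.

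The cost is plan wording and one power paragraph, with no new visits or data. The real downside is precision when sessions correlate highly. If 0.10 is a within-subject f², session 1 alone has 56% power at ρ = 0.7 against 84% for the pooled model. At ρ of 0 to 0.3 the loss is 0 to 3 points (0.971 against 0.971; 0.898 against 0.923). In exchange, the primary test does not depend on how the groups compare at week 2.
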